**Table 2.-1: Screening Procedural Outline (CA209923)**

Procedure	Screening a Visit	Baseline b Visit	Notes
Follicle Stimulating Hormone (FSH)	X		Women only. Refer to Appendix 4 for applicability.
Thyroid function testing		X	See note in Section 9.4.4
Adverse Event Reporting			
Monitor for Serious Adverse Events (SAEs)	X	X	Collection of SAEs begins when the informed consent form is signed.
Clinical Drug Supplies			
Randomize		X	Randomization can occur either on Day -1 or Day 1.
Clinical Assessments			
SOFA Score		X	Pre-dose, after participant is admitted to the ICU
Ventilator Usage		X	Record Start date, if applicable
Vasopressor Usage		X	Record Start date, if applicable
Dialysis Usage		X	Record Start date, if applicable

a Screening assessments must be performed within 10 days prior to Day 1 administration of randomized study treatment. If screening assessments other than labs are within 24 hours of dosing, then assessments performed for screening can be counted as both screening and baseline. Screening labs within 48 hours prior to dosing can be counted as both screening and baseline.

b Baseline assessments excluding labs must be within 24 hours prior to dosing. Baseline labs can be within 48 hours prior to dosing.

Procedure	WK 1 D1-7	WK2 D10	WK2 D14	WK3 D21	WK4 D28	WK6 D42	WK8 D56	WK10 D70	Indexa Hospitaliza tion Discharge	Studyb Discharge D90	Notes
Visit window		+/- 1 day	+/- 1 day	+/- 2 days	+/- 3 days	+/- 4 days	+/- 5 days	+/- 7 days		+/- 9 days	
Clinical Drug Supplies											
Randomize	X										Randomization can occur either on Day -1 or Day 1.
Study Drug Administration	X										Day 1.
Safety Assessments											
Physical Examination (PE)	X		X		X		X		X	X	Perform daily in Week 1, at Index Hospitalization Discharge, and at Study Discharge; Perform at other time points only if still hospitalized.
Physical Measurements									X	X	Weight only.
Vital Signs	X		X		X		X		X	X	Perform daily in Week 1, at Index Hospitalization Discharge, and at Study Discharge; Perform at other time points only if still hospitalized. See note in screening

Table 2.-2: On Treatment Procedural Outline (CA209923)											

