Procedure	WK 1 D1-7	WK2 D10	WK2 D14	WK3 D21	WK4 D28	WK6 D42	WK8 D56	WK10 D70	Indexa Hospitaliza tion Discharge	Studyb Discharge D90	Notes
											procedures.
Electrocardiogram (ECGs)	X		X		X		X		X	X	Perform at end of infusion on Day 1, at Index Hospitalization Discharge, and at Study Discharge; Perform at other time points only if still hospitalized.
Clinical safety laboratory tests	X	X	X	X	X		X		X	X	Days 1, 4 and 7 of week 1. See note in screening procedures and in Section 9.4.4
Pregnancy Test					X		X			X	WOCBP only. See note in Section 9.4.4.
Thyroid function testing							X		X	X	See note in Section 9.4.4
Adverse Event Reporting											
Monitor for Non-Serious Adverse Events	Collection of nonserious adverse events begins at initiation of study treatment. Adverse events must be collected up to Day 90.										
Monitor for Serious Adverse Events	See note in Screening procedures. SAEs must be collected up to Day 90.										
Other Assessments											

Table 2.-2: On Treatment Procedural Outline (CA209923)											
Procedure	WK 1 D1-7	WK2 D10	WK2 D14	WK3 D21	WK4 D28	WK6 D42	WK8 D56	WK10 D70	Indexa Hospitaliza tion Discharge	Studyb Discharge D90	Notes
Ventilator Usage	In days counting from the day of study treatment administration during participant’s index hospitalization.										
Vasopressor Usage	In days counting from the day of study treatment administration during participant’s index hospitalization.										
Dialysis Usage	In days counting from the day of study treatment administration during participant’s index hospitalization.										
Mortality	Date and primary cause of death.										
SOFA Score	Daily during the first week after study treatment administration, and weekly thereafter while participant is in ICU during participant’s index hospitalization.										
Length of ICU stay During Index Hospitalization	ICU discharge date during index hospitalization.										
Length of Index Hospitalization	Hospital discharge date during index hospitalization.										
Pharmacokinetic (PK) and Immunogenicity Assessments	See Section 9.5 for details and collection schedule.										

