#### **9.1 Efficacy Assessments**

Exploratory efficacy assessments include the following:

- Organ failure will be assessed by collection of SOFA score during index hospitalization

- Organ support will be assessed by duration of mechanical ventilation, vasopressor use, or dialysis use separately during the index hospitalization
- Length of stay in the ICU and in the hospital during the index hospitalization will be assessed

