### **9.2.4 Follow-up of AEs and SAEs**

- Nonserious AEs should be followed to resolution or stabilization, or reported as SAEs if they become serious (see [Appendix 3](#)).
- Follow-up is also required for nonserious AEs that cause interruption or discontinuation of study treatment and for those present at the end of study treatment as appropriate.
- All identified nonserious AEs must be recorded and described on the nonserious AE page of the CRF (paper or electronic). Completion of supplemental CRFs may be requested for AEs and/or laboratory abnormalities that are reported/identified during the course of the study.

After the initial AE/SAE report, the investigator is required to proactively follow each participant at subsequent visits/contacts. All SAEs, and non-serious immune-mediated AEs (as defined in [Section 9.2](#) will be followed until resolution, until the condition stabilizes, until the event is otherwise explained, or until the participant is lost to follow-up (as defined in [Section 8.3](#)).

Further information on follow-up procedures is given in [Appendix 3](#).

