Suspected transmission of an infectious agent (e.g., pathogenic or nonpathogenic) via the study treatment is an SAE.

Although pregnancy, overdose, cancer, and potential drug induced liver injury (DILI) are not always serious by regulatory definition, these events must be handled as SAEs. (See [Section 9.2.5](#) for reporting pregnancies).

In this study, the following events are study endpoints, per 21CFR 312.32 (c)(5), they are excluded from being reported as an SAE UNLESS the events are related to study drug.

- Death
- Hospitalization prolongation
- ICU admission
- Ventilator use
- Vasopressor use
- Dialysis use

These events will be recorded on other CRF pages instead of the SAE pages.

Any component of a study endpoint that is considered related to study therapy should be reported as SAE (e.g., death is an endpoint, if death occurred due to anaphylaxis, anaphylaxis must be reported).

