7.6 Efficacy

7.6.1 Exploratory Efficacy

Summary statistics will be provided for the following assessments by treatment and periodic time points. Listings will also be provided.

- Duration of mechanical ventilation, vasopressor use, or dialysis use separately during the index hospitalization.
- Sequential organ failure assessment (SOFA) scores at baseline and post-dosing time points, and change from baseline of SOFA scores during the index hospitalization.
- Length of ICU and hospital stay during index hospitalization.

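### Appendix 3 exempts unrelated ventilator, vasopressor and dialysis use from SAE reporting, and no visible safety table counts organ support newly started after dosing

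*Protocol*

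**What the plan says.** **Reporting.** Protocol Appendix 3 (Serious Adverse Events) lists six events as study endpoints: death, prolonged hospitalization, ICU admission, and ventilator, vasopressor and dialysis use. Of these it says "they are excluded from being reported as an SAE UNLESS the events are related to study drug", and then "These events will be recorded on other CRF pages instead of the SAE pages". It adds "Any component of a study endpoint that is considered related to study therapy should be reported as SAE", with death from anaphylaxis as the example.

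**Data collected.** At baseline, the screening schedule (Table 2.-1) asks for each type of support: "Record Start date, if applicable". After dosing, the on-treatment schedule (Table 2.-2) records each type "In days counting from the day of study treatment administration", for the index hospitalization only.

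**Analysis.** Protocol 9.1 lists these data as exploratory efficacy: "Organ support will be assessed by duration of mechanical ventilation, vasopressor use, or dialysis use separately during the index hospitalization". SAP 7.6.1 does the same, promising summary statistics and listings for "Duration of mechanical ventilation, vasopressor use, or dialysis use separately during the index hospitalization". SAP 8.2 supplies rules for counting days. It defines when a return to ventilation is a separate episode, but no count of episodes is planned.

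**Safety tables.** SAP 4.1 makes the incidence of AEs, SAEs, AEs leading to discontinuation, immune-mediated AEs and deaths the primary safety measure. SAP 7.7.1 gives death, which is on the same exemption list, its own all-cause table. SAP 7.7 shows no comparable table for organ support.

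**The concern.** AE and SAE incidence is a primary endpoint. In ICU patients given a checkpoint inhibitor, a new need for ventilation, vasopressors or dialysis is an event that a safety reviewer would want counted by dose, whatever the investigator thought of causality. The exemption moves unrelated cases to pages that are analysed as duration.

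Duration answers a different question. Vasopressor need and invasive ventilation are two of the three ways to qualify under inclusion criterion 2c, so some participants will be on support when dosed. Their remaining days on support are summarised together with the days of participants who started it after nivolumab. Two arms can look the same on duration and differ in new starts.

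The study has no data monitoring committee (protocol 5.1.1) and no placebo arm. The comparison between the two doses is its only randomised safety contrast, and for these events that contrast is not tabulated.

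**Working it through.** **1. The plan's own figure.** Protocol 10.1 and SAP 5 state an 80% probability of seeing at least one case of an AE with 10% incidence among 15 participants. 1 − 0.9^15 = 0.794, so the figure reproduces. It presumes that each event is counted.

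**2. Where an unrelated new start can appear.** Take a participant not ventilated at dosing who is intubated on Day 5 for a reason judged unrelated.
- The ventilator use itself is off the SAE page (Appendix 3) and goes to another CRF page.
- That page feeds the duration summary and listing in SAP 7.6.1.
- The respiratory failure behind it is not on the exemption list. It meets the AE definition in Appendix 3, and SAP 7.7 tabulates all recorded AEs, serious or not.
- The instruction about underlying events in Appendix 3 covers related ones only. Protocol 9.2.2 and the reporting part of Appendix 3 require every SAE regardless of causality, but neither mentions the exemption. Protocol 9.2.4 says "All identified nonserious AEs must be recorded and described on the nonserious AE page of the CRF", which settles nothing for an event that is serious.

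So the new start reaches a safety table only through the diagnosis, and sites may read the instruction differently. Even when the diagnosis is reported, the AE tables do not show that support was started.

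**3. What duration can hide.** All values here are assumed, apart from 15 per arm.
- Arm A: 10 ventilated at dosing, 6 further days each; 5 never ventilated. New starts: 0 of 5 at risk.
- Arm B: 5 ventilated at dosing, 6 further days each; 5 newly ventilated after dosing, 6 days each; 5 never ventilated. New starts: 5 of 10 at risk.
- Mean in both arms: 10 × 6 / 15 = 4.0 days. Median in both: 6 days. Range in both: 0 to 6 days.
- SD in both: √[(10 × (6 − 4)² + 5 × (0 − 4)²) / 14] = √(120/14) = 2.93 days.

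The duration summaries are identical, while new-start incidence is 0% against 50%.

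**4. What the missing table could show.** Its denominator is the number not on that support at dosing, which the documents do not give. Assume 5 to 15 per arm.
- Probability of at least one new start at a true 10% rate, 1 − 0.9^n: 41% (n = 5), 65% (n = 10), 79% (n = 15).
- Exact two-sided 95% upper limit when none is seen, 1 − 0.025^(1/n): 52%, 31%, 22%.

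The table would be descriptive and imprecise.

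**The case against.** A reader might infer that organ support started after dosing is never counted as a safety event. The documents do not support that. Related cases remain SAEs. The exemption names the support measure and not the illness behind it, and several rules call for the illness to be recorded: the causality-free AE definition in Appendix 3, the all-SAE rule in protocol 9.2.2, laboratory abnormalities needing corrective treatment (9.2.7), and significant worsening on any safety assessment (9.2.9).

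A reader might also infer that an unrecognised pneumonitis or nephritis would go unseen. That is too strong as well. The first summary in SAP 7.7.5 covers every listed term without requiring immune-modulating treatment or an immune cause, and the list in SAP Appendix 2 includes pneumonitis, interstitial lung disease, acute kidney injury and renal failure. SOFA change, laboratory shift tables and by-participant listings give further indirect information, and listings of about 30 people can be read case by case.

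Other fair points:
- The example is constructed, and the study plans no between-arm test. Even 3 of 15 against 0 of 15 gives a two-sided Fisher p of 2 × 455/4060 = 0.22.
- Both arms receive nivolumab, so background new starts have no control.
- Calendar days cannot place a Day 1 start before or after the infusion, and SAP 8.2 itself allows for hours not being recorded.
- The exploratory rows of protocol Table 4.-1 are redacted and the Data Presentation Plan is not available, so one can say only that no such table is visible.

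What survives all this is that none of these outputs is an incidence of newly started support by dose, and that the route through the diagnosis depends on an instruction that is unclear for unrelated events.

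**Conclusion.** The point holds in limited form. Read as written, Appendix 3 takes unrelated new ventilator, vasopressor and dialysis use out of the all-cause SAE incidence. The visible substitute is duration with listings, and its summaries can be identical in arms with different new-start rates. The plan closes the same gap for death and leaves it open for organ support. The pages also do not settle where an unrelated underlying event is recorded.

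It does not follow that these events are lost to safety review, because the underlying conditions remain reportable and are tabulated when reported. Nor can the documents say how many new starts would be missed: that depends on how many participants are off each support at dosing and on how sites read Appendix 3, and neither is given.

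This is a cheap improvement to a descriptive phase 1b plan. It does not affect the sample size or the PK objective.

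**What to change.** **SAP 7.7.** Add a descriptive table, by dose and total, for invasive ventilation, vasopressors and renal replacement therapy separately: the number and percentage of participants with a first start after dosing, among those not on that support at dosing, during the index hospitalization.
- Derive it by calendar day from the recorded start dates and support days. Show Day 1 starts on their own line where the time relative to the infusion is unknown.
- Add restarts for ventilation and renal replacement therapy, using the support-free gaps in SAP 8.2 (48 hours or 2 days; 72 hours or 3 days). SAP 8.2 sets no gap for vasopressors, so give first starts only.
- Place it beside the SAE tables and keep the duration summaries as exploratory efficacy.

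**Protocol.** Reconcile the exemption in Appendix 3 with protocol 9.2.2 and with the SAE reporting part of Appendix 3, so that sites know where to record an unrelated condition that leads to organ support.

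**Cost.** SAP wording, one derived table and a clarification for sites. No new data should be needed, provided the CRF dates the support days; the day and gap rules in SAP 8.2 presuppose this, but the CRF is not among the documents. The downside is one more table with small denominators and no placebo comparison. It should be labelled as signal display. Support started in a later admission stays outside it, because these data stop with the index hospitalization.

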## EVALUATING AES AND SAES

### Assessment of Causality

The causal relationship to study drug is determined by a physician and should be used to assess all adverse events (AE). The causal relationship can be one of the following:

Related: There is a reasonable causal relationship between study drug administration and the AE.

Not related: There is not a reasonable causal relationship between study drug administration and the AE.

The term "reasonable causal relationship" means there is evidence to suggest a causal relationship.

### Follow-up of AEs and SAES

If only limited information is initially available, follow-up reports are required. (Note: Follow-up SAE reports must include the same investigator term(s) initially reported.)

If an ongoing SAE changes in its intensity or relationship to study drug or if new information becomes available, the SAE report must be updated and submitted within 24 hours to BMS (or designee) using the same procedure used for transmitting the initial

SAE report.

All SAEs must be followed to resolution or stabilization.

## REPORTING OF SAES TO SPONSOR OR DESIGNEE

- SAEs, whether related or not related to study drug, and pregnancies must be reported to BMS (or designee) within 24 hours of awareness of the event.
- SAEs must be recorded on the SAE Report Form; pregnancies on a Pregnancy Surveillance Form (electronic or paper forms).
- The preferred method for SAE data reporting collection is through the eCRF.
- The paper SAE/pregnancy surveillance forms are only intended as a back-up option when the eCRF system is not functioning.
  - In this case, the paper forms are to be transmitted via email or confirmed facsimile (fax) transmission to:

**SAE Email Address: Refer to Contact Information list.**

**SAE Facsimile Number: Refer to Contact Information list.**

For studies capturing SAEs through electronic data capture (EDC), electronic submission is the required method for reporting. In the event the electronic system is unavailable for transmission, paper forms must be used and submitted immediately. When paper forms are used, the original paper forms are to remain on site.

**SAE Telephone Contact** (required for SAE and pregnancy reporting): Refer to Contact Information list

## **APPENDIX 4 WOMEN OF CHILDBEARING POTENTIAL DEFINITIONS AND METHODS OF CONTRACEPTION**

### **DEFINITIONS**

#### **Woman of Childbearing Potential (WOCBP)**

A woman is considered fertile following menarche and until becoming post-menopausal unless permanently sterile. Permanent sterilization methods include hysterectomy, bilateral salpingectomy, and bilateral oophorectomy.

#### **Women in the following categories are not considered WOCBP**

- Premenarchal
- Premenopausal female with 1 of the following:
  - Documented hysterectomy
  - Documented bilateral salpingectomy
  - Documented bilateral oophorectomy

Note: Documentation can come from the site personnel's review of the participant's medical records, medical examination, or medical history interview.

- Postmenopausal female
  - A postmenopausal state is defined as 12 months of amenorrhea in a woman over age 45 years in the absence of other biological or physiological causes. In addition, females under the age of 55 years must have a serum follicle stimulating hormone, (FSH) level > 40 mIU/mL to confirm menopause.

Note: Females treated with hormone replacement therapy, (HRT) are likely to have artificially suppressed FSH levels and may require a washout period in order to obtain a physiologic FSH level. The duration of the washout period is a function of the type of HRT used. The duration of the washout period below are suggested guidelines and the investigators should use their judgement in checking serum FSH levels.

- 1 week minimum for vaginal hormonal products (rings, creams, gels)
- 4 week minimum for transdermal products
- 8 week minimum for oral products

Other parenteral products may require washout periods as long as 6 months. If the serum FSH level is > 40 mIU/ml at any time during the washout period, the woman can be considered postmenopausal.

### **CONTRACEPTION GUIDANCE FOR FEMALE PARTICIPANTS OF CHILD BEARING POTENTIAL**

One of the highly effective methods of contraception listed below is required during study duration and until the end of relevant systemic exposure, defined as 4 months after the end of study treatment, plus 30 days (a total of 5 months).

Local laws and regulations may require use of alternative and/or additional contraception methods.

Highly Effective Contraceptive Methods That Are User Dependent
 
Failure rate of <1% per year when used consistently and correctly.a

 
• Combined (estrogen- and progestogen-containing) hormonal contraception associated with inhibition of ovulationb 
 
– oral
 
– intravaginal
 
– transdermal
 
 
 

 
• Progestogen-only hormonal contraception associated with inhibition of ovulationb 
 
– oral
 
– injectable
 
 
 

Highly Effective Methods That Are User Independent

 
• Implantable progestogen-only hormonal contraception associated with inhibition of ovulationb
 
• Intrauterine device (IUD)c
 
• Intrauterine hormone-releasing system (IUS)c
 
• Bilateral tubal occlusion
 

 
• Vasectomized partner
 
 
A vasectomized partner is a highly effective contraception method provided that the partner is the sole male sexual partner of the WOCBP and the absence of sperm has been confirmed. If not, an additional highly effective method of contraception should be used.


 
• Sexual abstinence
 
 
Sexual abstinence is considered a highly effective method only if defined as refraining from heterosexual intercourse during the entire period of risk associated with the study drug. The reliability of sexual abstinence needs to be evaluated in relation to the duration of the study and the preferred and usual lifestyle of the participant.
 
 
• It is not necessary to use any other method of contraception when complete abstinence is elected.
 
• WOCBP participants who choose complete abstinence must continue to have pregnancy tests, as specified in Section 2.
 
• Acceptable alternate methods of highly effective contraception must be discussed in the event that the WOCBP participants chooses to forego complete abstinence
 

**NOTES:**

- a Typical use failure rates may differ from those when used consistently and correctly. Use should be consistent with local regulations regarding the use of contraceptive methods for participants participating in clinical studies.
- b Hormonal contraception may be susceptible to interaction with the study drug, which may reduce the efficacy of the contraceptive method. Hormonal contraception is permissible only when there is sufficient evidence that the IMP and other study medications will not alter hormonal exposures such that contraception would be ineffective or result in increased exposures that could be potentially hazardous. In this case, alternative methods of contraception should be utilized.
- c Intrauterine devices and intrauterine hormone releasing systems are acceptable methods of contraception in the absence of definitive drug interaction studies when hormone exposures from intrauterine devices do not alter contraception effectiveness

